7.1.2. Inclusion and exclusion criteria

The population enrolled in the study will be HIV infected individuals meeting all screening and inclusion criteria, and none of the exclusion criteria listed in Tables 3 and 4.

Only patients who meet all the following selection criteria can be enrolled in the study.

Table 3: Inclusion Criteria

HCV RNA loads	Have evidence of chronic HCV infection for at least the last 6 months before study entry (at least one detectable HCV viral loads, i.e. ≥ 17 IU/mL, with an antibody test positive at least 6 months before the HCV RNA load).
Liver	Fibrosis Stage F2-3-4 as determined by transient elastography (Fibroscan or other similar equipment). During the first part of the study, priority will be given to patients with Fibrosis Stage F2-3.
Contraception	Negative pregnancy test (on the day of inclusion).

Table 4: Exclusion criteria

Hematology	Anemia (hemoglobin level < 10 g/dL) Platelets $< 50,000$ /mm ³
Liver	Evidence of decompensated liver disease manifested by presence or history of ascites, variceal bleeding, or hepatic encephalopathy or Child-Pugh score greater than A (Participants with documented or suspected hepatic cirrhosis must have either serum alpha-fetoprotein level of 50 ng/ml or less within 24 weeks prior to study entry; or serum alpha-fetoprotein greater than 50 ng/ml but no greater than 400 ng/ml with an imaging procedure that shows no evidence of a hepatic tumor, both obtained within 24 weeks prior to study entry.) Suspicion or evidence of liver cancer. Hepatitis B (this exclusion criteria will be applied only to the first part of the protocol).
Endocrinology	Uncontrolled diabetes. Uncontrolled thyroid dysfunction (thyroid-stimulating hormone, TSH).
Ophthalmology	Retinopathy.
Kidney function	Creatinine clearance < 50 mL/min (Cockcroft).
Immunology	Disease associated with the immune system (such as Crohn's disease, ulcerative colitis, active rheumatoid arthritis, lupus, idiopathic thrombocytopenic purpura, autoimmune hemolytic anemia, cryoglobulinemia with clinical manifestations including leukocytoclastic vasculitis, scleroderma, or severe psoriasis).
Cardiology	Significant heart problems, such as active symptomatic coronary artery disease.
Neurologic and psychiatric conditions	Have uncontrolled seizures. Have a history of severe mental problems. Uncontrolled depression or other psychiatric disorder, such as untreated Grade 3 psychiatric disorder, Grade 3 disorder not amenable to medical intervention. Both selective serotonin reuptake inhibitors and other classes of antidepressants are allowed. Active drug or alcohol abuse or dependence that, in the opinion of the study investigator, could interfere with adherence to study requirements.

Other exclusion criteria related to the use of ribavirin and peg-interferon
	
Pregnancy or no contraception if participant is a woman. Pregnancy or no contraception in the female partner of a male participant. No use of condoms, sperm donation or participation in any other fertilization procedures if participant is a man. Breastfeeding. Other contra-indications to ribavirin (see Package Insert). Allergy to peg-interferon or ribavirin. Current administration of didanosine, zidovudine or stavudine. Have taken the following drugs within 6 weeks before study entry: rifampin, rifabutin, pyrazinamide, isoniazid, G-CSF (filgrastim), GM-CSF (sargramostim), or ganciclovir.

Others
	
Have taken any of the following drugs within 6 months before study entry: interleukins, interferons, therapeutic HIV vaccine, thalidomide, pentoxifylline, dinitrochlorobenzene (DNCB), thymosin alpha, thymopentininosiplex, polyribonucleoside, ditiocarb sodium, hydroxyurea, systemic corticosteroids, azathioprine, 6-mercaptopurine, cyclosporin A, or any investigational drug. Any conditions that, in the investigator’s judgment, may compromise the follow up.

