A total of 60 patients will be enrolled in the study: 15 HCV-HIV co-infected patients in a first part and 45 patients in a second part, if funding is obtained from the GFATM and/or other funding sources.

STUDY POPULATION

Screening: HIV infected patients with a positive anti-HCV test will be approached for screening if they are at least 18 years old, participate in the PHPT cohort study, have evidence of control of HIV replication and have a CD4 cell count ≥ 200 cells/mm³ if currently receiving antiretroviral HIV treatment (on the same anti-HIV regimen for at least 12 weeks); or HIV RNA load ≤ 5000 copies/ml CD4 cells ≥ 500 cells/mm³ if not receiving antiretroviral treatment.

Inclusion Criteria

- Evidence of chronic HCV infection for at least 6 months before study entry (at least one detectable HCV viral load, i.e. ≥ 17 IU/mL, with an antibody test positive at least 6 months before the HCV RNA load result)
- Fibrosis Stage F2-3-4 determined by transient elastography (Fibroscan or other similar equipment). During the first part of the study, priority will be given to patients with Fibrosis Stage F2-3.
- Negative pregnancy test (on the day of inclusion).

Main exclusion criteria (see complete list in the protocol)

- Anemia and thrombocytopenia

- Severe liver damage, advanced stage cirrhosis or cancer
- Uncontrolled diabetes, Uncontrolled thyroid dysfunction
- Retinopathy
- Creatinine clearance <50 mL/min (Cockcroft)
- Disease associated with the immune system
- Significant heart problems
- Severe neuropsychiatric conditions Contra-indication to study treatment (including pregnancy or lack of effective contraception in the participant or female partner)
- Other exclusion criteria related to the use of ribavirin and peg-interferon
- Any conditions that, in the investigator's judgment, may compromise the follow up.

FOLLOW UP AND STUDY PROCEDURES

During the screening process, the following assessments will be performed in this order to determine eligibility for HCV treatment:

- HCV RNA load (if undetectable, the screening process will be terminated)
- Fibrosis assessment by transient elastography
- SGPT/ALT, SGOT/AST, gamma glutamyl transferase (GGT), conjugated and unconjugated bilirubin, albumin, alkaline phosphatase, glucose, triglycerides, prothrombin time (PT), HDL & LDL cholesterol, alpha fetoprotein (AFP), thyroid-stimulating hormone (TSH), vitamin D plasma level, abdominal sonogram

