7.2. Implementation, data collection and monitoring procedures

7.2.1. Assessments

7.2.1.1 Screening Assessments

The assessments listed in Table 5 will be performed to determine if a subject can participate in the study.

The **first investigation** performed will be the measurement of HCV RNA load to assess the need for treatment. Only patients with detectable HCV RNA load will continue to be assessed for potential participation in the study.

Table 5: Screening assessments

Category	Examination
Virology	HCV RNA load
Medical history	Interview and/or chart review
Liver imaging	Fibrosis assessment by transient elastography Liver ultrasound exam
Clinical chemistries	SGPT/ALT, SGOT/AST, gamma glutamyl transferase, bilirubin (conjugated, unconjugated), Albumin, Alkaline phosphatase, glucose, triglycerides, prothrombin time (PT), HDL & LDL cholesterol, alpha fetoprotein (AFP), creatinine, urine protein, thyroid-stimulating hormone (TSH), vitamin D level
Hematology	CBC including platelets
Ophthalmology	Ophthalmologic examination (fundus) if diabetes mellitus or hypertension
Central nervous system	Beck Inventory Depression scale (nurse, counselor)

Heart, lungs	Electrocardiogram, chest X-ray,
Contraception	Pregnancy test (for female participant or partner of male participant) if childbearing age
Host genetic	IL28B polymorphism

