7.2.1.2 Assessments during the study

The detailed assessments are listed in Table 6.

Fibrosis assessment. For enrollment, fibrosis assessment will be performed using the transient elastography ultrasound based technique. It measures the stiffness of the liver, which is well correlated with the fibrosis stage assessed by liver biopsy. It has been extensively used as a non-invasive method for detection of cirrhosis in patients with chronic liver disease (Foucher et al., 2006). In addition, to further characterize patients enrolled in this study, two scores will be calculated:

- the AST to platelets ratio index (APRI score) will be calculated at baseline as it has been shown to predict both significant fibrosis and cirrhosis in patients with chronic hepatitis C (Wai et al., 2003).
- The FIB4 score (Bruno et al., 2011), which has also been used for the evaluation of fibrosis. A cut-off value >3.25 is consistent with significant (F2–F4) fibrosis; its sensitivity was 70% and specificity 86–97% in a study conducted in HIV/HCV co-infected persons (Sterling et al., 2006). It is calculated using the following formula:

$$(\text{age [years]} \times \text{AST [U/L]}) / (\text{platelet count} [\times 10^9/\text{L}] \times (\text{ALT [U/L]}^{1/2}))$$

Depressive symptoms will be screened using the Beck Depression Inventory (Thai version). This auto-administered scale, which consists of 21 questions to assess the severity of depression, has been extensively used in various studies related to HCV treatment.

Table 6: Follow up Assessments

	Scr.	Baseline	Wk2	Wk4	Wk8	Wk12	Wk16	Wk20	Wk24	Wk28	Wk32	Wk36	Wk40	Wk44	Wk48	6 months post-Treatment
HCV RNA load	X			X		X			X						X	X
Counseling	X	X	X	X					X						X	X
Beck's Depression Inventory scale (more often if necessary, see Section 7.2.2.2, page 20)	X			X		X			X			X			X	
SF-36 Scale (quality of life)		X							X						X	X
Pregnancy test (for female participant or partner of male participant) if childbearing age	X	X		X	X	X	X	X	X	X	X	X	X	X	X	X
CBC with differential	X	X	X	X	X	X	X		X		X		X		X	X
SGPT (ALT)	X	X		X		X		X		X		X		X	X	X
Alkaline phosphatase, albumin, bilirubin (conjugated, unconjugated), gamma-glutamyl-transferase (GGT), HDL, LDL cholesterol, triglyceride, prothrombin time, SGOT (AST), proteinuria (random)	X														X	X
Electrolytes (Na+, K+, Cl-, HCO3-)		X				X			X						X	
Creatinine	X	X		X	X	X		X		X		X			X	X
Glucose	X	X				X			X						X	
TSH	X	X							X						X	

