7.3. Study drugs

Peg-interferon alpha 2-b

First dose: 1.5 micrograms/kg (subcutaneous injection)

Mode of administration:

The study nurse will read with each patient the booklet 'Patient diary for PEG-INTRON monotherapy or PEG-INTRON and Rebetol' in Thai language (MSD), which provides information on peg interferon and ribavirin and specific instructions for the preparation and injection of peg-interferon. The nurse will give each patient this booklet.

For the first injection, the study site nurse at the hospital will prepare the syringe and proceed to the injection, observe and record the occurrence of side effect for at least the first 3 hours after administration. The second injection, one week later, can be done by the patient, under supervision of an experienced nurse at the hospital. The nurse will evaluate if the patient is able and willing to perform following injections by him/herself. As long as the patient does not appear able or willing to perform injections, he/she will be welcome to return to the hospital for injections.

The patient will be provided with an Injection Card, reporting all the injections received with date, time and person who administered the dose. During the first weeks, the nurses will regularly call the patient to make sure that the drugs are correctly administered and how to deal with adverse events.

Ribavirin

First dose:

- For genotypes 2, 3: ribavirin 400 mg in the morning and in the evening (i.e. 800 mg daily).
- For genotypes 1, 4, 5 and 6: the ribavirin dose is
 - 800 mg/day, if bodyweight <65 kg,
 - 1000 mg/day, if bodyweight between 66–80 kg,
 - 1200 mg/day, if bodyweight between 81–105 kg,
 - 1400 mg/day, if bodyweight >105 kg.

Mode of administration:

Ribavirin should be given in two divided doses (e.g. 400/400 mg bid, 600/400 mg bid, 600/600 mg bid, or 800/600 mg bid) at the end of the meals, in the morning and evening.

At each visit, patients will be asked to bring back the remaining study drug's vials or bottles (Peg-interferon alpha 2-b and ribavirin) even if they are empty to assess adherence.

The study site pharmacist will be responsible for storage, dispensation including drug counseling, and drug accountability.

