Dry skin/ rashes	
 • Avoiding long, hot showers or baths • Using moisturizing soaps • Using moisturizing lotion after showers • Using mild unscented laundry detergents and avoiding fabric softeners • Using sunscreen • Trying rubbing or pressing on the itchy areas rather than scratching • Prescribe petroleum jelly or other agents on dry, itchy areas
Hair thinning or hair loss	
 • Avoiding harsh hair products such as dyes, perms, gels, sprays and mousses • Using a mild shampoo such as baby shampoo • Avoiding braiding hair; using a wide-tooth comb or soft brush • Wearing a cap, scarf, turban or wig
Injection site reactions	
 • Before injecting, warming the medicine by gently rolling the syringe in the hands for a minute • Rotating/alternating the injection site - thigh, upper arm and abdomen. If thin, using the thigh area might help • Not doing injection into an area that is irritated, bruised or red • Not doing rub injection site • Applying a cold pack • Hydrocortisone cream or other medications can be prescribe to help

Modification of treatment in case of laboratory abnormality:

Peg-interferon alfa-2b must be stopped if: Laboratory exam	Value	Yes	Dose modification
Hemoglobin	< 8.5 g/dL		→ STOP Peg-interferon in case of any of these events
Hemoglobin if history of stable cardiac disease * 4 weeks of a dose reduction	< 12 g/dL*		
WBC	< 1000/mm ³		
Neutrophils	< 500/mm ³		
Platelets	< 25000/mm ³		

Laboratory exam	Value	Yes	Dose modification
Hemoglobin if history of stable cardiac disease	≥ 2 g/dL decrease since the last visit		→ Reduce dose of Peg-interferon of 0.5 mcg/kg If one of these events is verified
WBC	< 1500/mm ³		
Neutrophils	< 750/mm ³		
Platelets	< 50000/mm ³		

Ribavirin dose reduction

Laboratory exam	Value	Yes	Dose modification
Hemoglobin	< 10 g/dL		→ Reduce dose of Ribavirin If one of these events is verified
Hemoglobin if history of stable cardiac disease	≥ 2 g/dL decrease since last visit		

Dose reduction:

If previous dose = 400 mg morning/200 mg evening → **STOP Ribavirin and contact** ☎

If previous dose = 400 mg morning/400 mg evening → Decrease to 400 mg morning/200 mg evening

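### No white-cell or neutrophil limit applies at entry, and the protocol does not say whether Appendix 4's limits for these counts apply before the first peg-interferon dose

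*Combined protocol and SAP*

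**What the plan says.** Table 4 in section 7.1.2 gives the hematology exclusions as "Anemia (hemoglobin level < 10 g/dL) Platelets $< 50,000$ /mm"³. The Project Summary (section 3) lists "Anemia and thrombocytopenia" and no other blood-count exclusion. Tables 2 and 3 and the remaining rows of Table 4 contain no white-cell or neutrophil limit.

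Two general exclusions bear on the point. The Project Summary excludes "Contra-indication to study treatment", which covers both drugs. Table 4 has "Other contra-indications to ribavirin (see Package Insert). Allergy to peg-interferon or ribavirin", so it points to a package insert for ribavirin only.

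Section 7.3 begins the peg-interferon entry with "First dose: 1.5 micrograms/kg (subcutaneous injection" and adds no blood-count condition.

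The laboratory tables in Appendix 4 require peg-interferon to be stopped at white cells below 1000, neutrophils below 500 or platelets below 25,000/mm³. At white cells below 1500, neutrophils below 750 or platelets below 50,000/mm³ the instruction is "Reduce dose of Peg-interferon of 0.5 mcg/kg If one of these events is verified".

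Table 6 schedules "CBC with differential" at screening, at baseline and again at week 2.

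**The concern.** The entry limits that exist line up with Appendix 4. The platelet exclusion equals the peg-interferon reduction limit, and the hemoglobin exclusion equals the ribavirin reduction limit. On those two counts nobody should enter already needing a reduction. White cells and neutrophils are in the same Appendix 4 tables but have no entry counterpart, and the protocol gives no reason for the difference.

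The starting dose does not settle it. Section 7.3 gives one weight-based first dose. Appendix 4 is headed as modification of treatment, and its white-cell and neutrophil rows do not say whether a pre-treatment result counts. A site with a low baseline neutrophil count therefore has two instructions and no statement of which governs.

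Patient safety is what is at stake: full-dose interferon in someone whose count would, once on treatment, trigger a reduction or a stop.

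**Working it through.** No figure in the plan needs reproducing. The check sets the limits side by side and then counts doses.

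**Limits (Table 4 for entry; Appendix 4 for reduce and stop)**

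| Count | Excluded at entry | Reduce | Stop peg-interferon |
|---|---|---|---|
| Hemoglobin (no cardiac history) | < 10 g/dL | < 10 g/dL (ribavirin) | < 8.5 g/dL |
| Platelets/mm³ | < 50,000 | < 50,000 (peg-interferon) | < 25,000 |
| White cells/mm³ | none | < 1500 (peg-interferon) | < 1000 |
| Neutrophils/mm³ | none | < 750 (peg-interferon) | < 500 |

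Appendix 4 uses four counts. Two have an entry limit, so 4 − 2 = 2 do not.

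**Ranges without an entry rule.** The reduction band is white cells 1000–1499 or neutrophils 500–749/mm³. The stop range is white cells below 1000 or neutrophils below 500/mm³.

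**Example.** A patient with neutrophils 600/mm³, hemoglobin 12 g/dL and platelets 80,000/mm³ meets no written blood-count exclusion, yet is below the 750/mm³ reduction limit.

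**Doses before the first on-treatment count.** Injections are weekly (section 7.3) and the first on-treatment count is at week 2 (Table 6). The doses at weeks 0 and 1 come before it, which makes two.

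- Full dose: 2 × 1.5 = 3.0 mcg/kg.
- Reduced by 0.5: 2 × (1.5 − 0.5) = 2.0 mcg/kg; ratio 3.0/2.0 = 1.5.
- Reduced to 0.5, if the Appendix 4 wording means that: 2 × 0.5 = 1.0 mcg/kg; ratio 3.0/1.0 = 3.
- Stop range, if the stop rule applied at baseline: 0 against 3.0 mcg/kg.

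The second line is the more natural reading, because section 7.2.2.2 gives 1.5 to 1.0 mcg/kg as the usual first step (for depression).

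**Does anything else supply a floor?** The CD4 criterion in Table 2 (at least 200/mm³ on antiretrovirals, at least 500/mm³ off them) sets no neutrophil floor, and the 200 limit is waived for hypersplenism. The investigator-judgment exclusion in Table 4 concerns conditions that threaten follow-up. Section 7.1.3 lets a co-investigator end participation for the patient's health, but names no count. None of these sets a white-cell or neutrophil limit.

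**The case against.** The strongest reply is that Appendix 4 may already apply. Its white-cell and neutrophil rows carry no time condition, a count with differential is available at baseline, and a specific laboratory rule can reasonably qualify a standard first dose. If so, the low-count patient is dealt with. This stands as a possible reading, but it cannot be confirmed. Some rows of the same tables are plainly on-treatment (a hemoglobin fall since the last visit), and no text says that the tables qualify section 7.3. If Appendix 4 is instead purely on-treatment, treating its limits as entry limits is an inference. Either way a sentence is missing.

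A reader might infer that the reduction band is a definite gap and only the stop range is unclear. The documents do not support that distinction: both sets of rows lack a time condition for these counts, so both are unclear in the same way.

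Second, other criteria shrink the group. Zidovudine is barred, as are ganciclovir and G-CSF or GM-CSF within 6 weeks; liver disease beyond Child-Pugh A is excluded; and there is a CD4 floor. Off antiretrovirals, CD4 of at least 500 with white cells below 1500 leaves under 1500 − 500 = 1000/mm³ for all other white cells. This stands. It makes such patients fewer but does not rule them out.

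Third, the Project Summary's contraindication exclusion covers peg-interferon, and its package insert is cited but not reproduced. It may close part of the gap.

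Fourth, the omission may be deliberate: the study admits F4 disease and tolerates hypersplenism. This also stands, and it argues against making a new exclusion the only remedy.

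Finally, a reader might take "CBC including platelets" in Table 5 to mean that no differential is done at screening. Table 6 specifies one, so that row needs no change.

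**Conclusion.** The point holds as a gap in the pre-dose rule. Entry is tied to Appendix 4 for hemoglobin and platelets but not for white cells or neutrophils, and the protocol does not say whether the Appendix 4 limits for those two counts (1500 and 750 to reduce, 1000 and 500 to stop, per mm³) apply before dose 1. Following section 7.3 literally exposes a patient in the reduction band to 1.5 times the reduced amount over two injections, or 3 times on the less natural reading of the reduction wording.

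These are dose ratios, not estimates of harm. The documents give no frequency, a clinician may well hold or lower the dose unprompted, and the exposure lasts until the week 2 count. A reader might go on to infer bias in the sustained response rate or in the discontinuation endpoint; nothing in the documents supports either. Confidence is moderate because the peg-interferon insert is not available here.

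**What to change.** State in section 7.3 or Appendix 4 that the Appendix 4 white-cell and neutrophil limits are checked on the screening or baseline count with differential before the first dose, and give the action:

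- White cells below 1000 or neutrophils below 500/mm³: do not start.
- White cells 1000–1499 or neutrophils 500–749/mm³: either exclude in Table 4 or start at 1.0 mcg/kg, as the study clinicians choose.

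The cost is one or two sentences, plus a line in Table 4 if exclusion is chosen. No extra test is needed. The downside is that a few patients, possibly some with compensated F4 disease or hypersplenism, are excluded or start at a lower dose. A patient just above the limits can still fall below them on treatment; the week 2 count remains the safeguard for that.

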7.1.3. Discontinuation criteria

Participation in the study. A study site co-investigator may decide to end a subject’s participation in the study if, in his/her own judgment, such a participation would be detrimental to a subject’s health or well-being. However, all efforts should be made to inform the study team and discuss options prior such a decision.

Discontinuation of treatment. For the discontinuation of therapy prior to week 48, the protocol will follow the recommendations of the “Guide for evaluation and treatment of Hepatitis C in adults co-infected with HIV” (See Figure 1) (Sulkowski, Cheever, & Spach, 2011), i.e.:

“HCV treatment should be stopped earlier than 48 weeks if on-treatment HCV RNA response futility criteria are met at treatment week 12 or 24.

Treatment should be discontinued in patients who at week 12 do not achieve an early partial virologic response ($\geq 2 \log_{10}$ decline in HCV RNA level from baseline) or complete virologic response (undetectable HCV RNA at treatment).

Patients who have an early virologic response, but do not achieve an undetectable HCV RNA at treatment week 12, should be re-tested at week 24. If HCV RNA levels remain detectable at week 24, treatment should be discontinued.

In addition, treatment may need to be discontinued in patients who develop severe adverse effects to treatment or intolerable treatment-related side effects.”

These patients will then continue to receive the standard of care, off treatment.

[figure not shown]

Figure 1: Decision tree for discontinuation of treatment

Discontinuation of the study. The study could be discontinued if required by Thailand health authorities or sponsors.

